10.4 Prior and Concomitant Medications

Medications are categorized as prior medication or concomitant medication based on the following rules:

- Any medication taken prior to blinded study phase start (first ICF signature) as recorded by the investigator is considered prior medication.
- Any medication **not** taken prior to blinded study phase start as recorded by the investigator is considered concomitant medication.
- Any medication taken prior to blinded study phase start as recorded by the investigator and for which "Ongoing" is ticked as "Yes" or "Unknown" is considered concomitant medication.

Note: A medication can be both prior and concomitant if it starts prior to trial start and is ongoing.

10.5 AEs

An AE is any untoward medical occurrence in a subject which does not necessarily have to have a causal relationship with the investigational product. In this trial, confirmed non-fatal cases of COVID-19 and complications/sequelae are not considered as AEs as they are captured on the CRF pages for COVID-19 illness which are expected outcomes of the trial and are analyzed as efficacy endpoints. Only for any complications and sequelae of COVID-19 illness not mentioned on the COVID-19 summary form in the electronic Case Report Form (eCRF), an AE form needs to be completed.

In this trial, for Phase 2b subjects, information on solicited local and systemic AEs occurring within 7 days after each CVnCoV vaccination and on unsolicited AEs occurring within 28 days after each CVnCoV vaccination are collected.

For all Phase 2b and Phase 3 subjects, information on medically attended AEs up to 6 months after second CVnCoV vaccination and SAEs, AESIs and AEs leading to vaccine withdrawal or trial discontinuation after the second CVnCoV vaccination to EOT Visit are recorded.

No other AEs require recording in the CRF.

The recording of AEs remains unchanged, irrespective of the subject rolling over to the OL-phase or not.

10.5.1 Treatment Emergent Adverse Events (TEAE)

A TEAE is any AE that first occurs or increases in severity or relationship to trial vaccine (CVnCoV/placebo) after the first dose of CVnCoV/placebo vaccine. AEs which change in severity or relationship to trial vaccine (CVnCoV/placebo) are assigned a new start date and captured as a new record in the CRF. Hence, an AE is defined as TEAEs if the start date/time is after the date/time of first CVnCoV/placebo vaccination. Imputed AE start date/time as defined in Section 10.3 is considered when assessing if an AE is treatment emergent. If the AE start date is still missing after applying imputation rules (i.e. missing year), the AE is considered treatment emergent and is assumed to occur within 28 days after any CVnCoV/placebo vaccination. However, it is not possible to link this event to a specific CVnCoV/placebo dose.

All Solicited AEs are considered treatment emergent, even in the case that (partially) missing or conflicting date/time information is recorded or imputed.

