Clinical Trial Protocol	CV-NCOV-004
CureVac AG	COVID-19 mRNA Vaccine

that the Investigator always makes an assessment of causality for every event before the initial transmission of the SAE data to the CRO.

The Investigator may change his/her opinion of causality in light of follow-up information and send a SAE follow-up report with the updated causality assessment.

The causality assessment is one of the criteria used when determining regulatory reporting requirements.

All local **solicited** symptoms are considered related to vaccination.

Recording of AEs and/or SAEs

AE and SAE Recording

- The Investigator is responsible for recording all AEs/SAEs observed during the trial i.e. from the time the subject gives informed consent until the end of the trial visit or until the last follow-up visit, for the period described in Table 6.
- When an AE/SAE occurs, it is the responsibility of the Investigator to review all documentation (e.g., hospital progress notes, laboratory reports, and diagnostics reports) related to the event.
- SAEs need to be reported to the CRO within 24 hours (see section Reporting of SAEs).
- It is not acceptable for the Investigator to send photocopies of the subject's medical records to the CRO in lieu of completion of the AE/SAE eCRF screen.
- There may be instances when copies of medical records for certain cases are requested by the CRO. In this case, all subject identifiers, with the exception of the subject number, will be redacted on the copies of the medical records before submission to the CRO.
- The Investigator will attempt to establish a diagnosis of the event based on signs, symptoms, and/or other clinical information. Whenever possible, the diagnosis (not the individual signs/symptoms) will be documented as the AE/SAE (except for COVID-19, which should not be recorded as an AE in this trial).
- AESIs and cases of overdose must be documented and medically assessed by the Investigator and the outcome described on the SAE/AESI/overdose/misuse report form.
- Pregnancy must be documented and medically assessed by the Investigator and the outcome described on the Pregnancy Report Form which is to be sent to the CRO.

Follow-up of Unsolicited AEs and SAEs

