10.5.4 Unsolicited AEs

Information on unsolicited AEs occurring on each CVnCoV/placebo vaccination day (i.e. dose 1 and 2) and the following 28 days after each CVnCoV/placebo dose are collected for Phase 2b subjects. Data is recorded in the eDiary by the subject to aid AE reporting. The investigator reviews the eDiary and records information on any AEs on the CRF.

Unsolicited AEs are assigned to first or second CVnCoV/placebo dose based on the (reported or imputed) AE date. Unsolicited AEs occurring before dose 2 are assigned to dose 1. Unsolicited AEs occurring after dose 2, are assigned to dose 2. Unsolicited AEs occurring on the day of dose 2 are assigned to either dose 1 or dose 2 as per the following rules:

- If the AE occurred on the day of dose 2 but before vaccination with dose 2, the AE is assigned to dose 1.
- If the AE occurred on the day of dose 2 but on or after vaccination with dose 2, it is assigned to dose 2.
- If the AE occurred on the day of dose 2 and it cannot be determined whether it occurred before, on or after vaccination with dose 2, it is assigned to dose 2.

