12.7 Safety Analyses

12.7.1 Adverse Events

Unsolicited AEs, including SAEs, and AESIs and solicited AEs integrated to or recorded on the CRF are coded using MedDRA Version 23.1 or higher, by SOC and PT.

Only TEAEs as defined in Section 10.5.1 are included in AE summaries. In AE listings, all AEs are included.

Solicited AEs occurring on the day of vaccination and the following 7 days are generally included in summaries if not otherwise stated.

Summaries of medically attended AEs only include those AEs that started up to 6 months after the second trial vaccination, see Section 10.5.6 for further details.

Note that for all summaries by SOC and PT, counting is by subject, not event and subjects are only counted once within each SOC and PT. However, if not stated otherwise, all summaries of unsolicited AEs include the number of AEs reported in each category and all events of a subject are then counted.

All AE summary tables are provided overall, by vaccine group, and by age group and vaccine group and are repeated separately in subjects seronegative at baseline and in subjects seropositive at baseline for SARS-CoV-2 N protein antibody levels (see Section 10.6.1).

In general, percentages are based on the number of subjects in the respective analysis set. In summary tables for AEs after the second vaccination, percentages are based on the number of subjects in the respective analysis set who have received the second vaccination.

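### SAP 10.5.1 re-dates an adverse event on any change, not only on an increase, so improving unsolicited events are counted again and can enter the wrong dose table or exposure group

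*SAP*

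**What the plan says.** SAP 10.5.1 makes three statements in sequence.

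- The concept: "A TEAE is any AE that first occurs or increases in severity or relationship to trial vaccine (CVnCoV/placebo) after the first dose".
- The recording rule for the CRF: "AEs which change in severity or relationship to trial vaccine (CVnCoV/placebo) are assigned a new start date and captured as a new record".
- The test: "Hence, an AE is defined as TEAEs if the start date/time is after the date/time of first CVnCoV/placebo vaccination".

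Other sections use the resulting date. SAP 10.5.4 assigns unsolicited AEs to a dose by AE date ("Unsolicited AEs occurring after dose 2, are assigned to dose 2"). SAP 10.5.6 applies the six-month limit for medically attended AEs to the start date. SAP 12.7.1.1 and 12.7.1.3 build the 28-day tables. SAP 12.7.7 uses the start date to place each AE in Placebo-only, CVnCoV-only, CVnCoV-AV or AV-only, without censoring, and these outputs replace the open-label safety analyses.

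SAP 12.7.1 sets the counting. In tables by SOC and PT, "counting is by subject, not event and subjects are only counted once within each SOC and PT", but "all summaries of unsolicited AEs include the number of AEs reported in each category and all events of a subject are then counted".

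Solicited AEs have their own safeguards. SAP 10.5.2 collapses overlapping same-day records that have the same relationship, and 10.5.3 ignores grade transitions when it computes duration.

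Protocol Appendix 10 says of causality: "The Investigator may change his/her opinion of causality in light of follow-up information". It directs that updated information be entered in the eCRF entry completed originally.

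**The concern.** The test on start date follows from the concept only if a new record is opened solely for an increase. The recording rule opens one for any change, so an AE that is getting better acquires a later start date and passes the test as a new event. Nothing in the SAP links or collapses such records for unsolicited AEs, SAEs, AESIs or medically attended AEs, although the equivalent problem was recognised for solicited AEs.

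Occurrence, intensity and relationship of these events are primary safety endpoints. For improvements the error has one direction, because a re-dated record can only move towards a later exposure: dose 1 events appear under dose 2, and events that began before an AV appear under CVnCoV-AV or AV-only. The second path matters because the protocol reports that approximately 49% of subjects had already received an AV by 18 November 2021.

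**Working it through.** The plan states no figure for this rule, so there is nothing to reproduce. The check applies the rules literally to constructed events, with dose 1 on Day 1 and dose 2 on Day 29 as scheduled. Time since a dose is the AE day minus the dose day, and a record is in that dose's 28-day window if the result is at most 28.

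**A. Improvement across dose 2.** Grade 2 on Day 10, Grade 1 on Day 31.
- First record: 10 − 1 = 9 days after dose 1, so dose 1.
- Second record: 31 − 29 = 2 days after dose 2, so dose 2.
- Literal result: 2 events, with the subject in both the dose 1 and dose 2 tables. Percentages in the dose 2 table are based on subjects who received dose 2, so its numerator gains one subject.
- Under the TEAE concept: 1 event, dose 1 only.

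**B. Improvement within one window.** Grade 2 on Day 5, Grade 1 on Day 12.
- 5 − 1 = 4 and 12 − 1 = 11, so both records belong to dose 1.
- Literal result: 2 events, but 1 subject in the PT row and maximum Grade 2, as under the concept. Only the event count changes.

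**C. Improvement after an AV.** AESI on Day 60 after CVnCoV, AV on Day 150, improvement on Day 160.
- 60 < 150, so the first record is CVnCoV-only. 160 > 150, so the second is CVnCoV-AV.
- Literal result in the 12.7.7 outputs: 2 events, one in each group. Under the concept: 1 event, CVnCoV-only.
- In the main safety analyses, SAP 10.11 censors from the day after unblinding or AV receipt, so the Day 160 record does not enter.

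**D. Onset before dose 1.** AE starts three days before dose 1 and is milder on Day 2.
- The new start date is after dose 1, so the start-date test makes it a TEAE; the concept does not.
- Protocol 10.3.7 records AEs that start before dose 1 as medical history, so this case arises only where that instruction is not followed.

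**Medically attended AEs.** A milder record dated after the six-month limit falls outside it while the original stays inside. No subject is lost. A milder record inside the limit adds an event.

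**Event counts in general.** If a share q of unsolicited AEs has one recorded decrease or downward re-assessment, the total number of events is multiplied by 1 + q. The documents give no q. As pure assumption, q = 5%, 10%, 20% and 30% give 1.05, 1.10, 1.20 and 1.30. Increases do not belong in q, because the SAP's concept treats them as new TEAEs.

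**The case against.** The case on the other side is substantial. The primary safety estimand is the number and percentage of subjects, not events, and a subject counts once per SOC and PT. Tables by maximum severity absorb a later, milder record. Protocol 10.3.7 takes the maximal severity and strongest relationship when an AE recurs within 28 days of one vaccination. The main analyses are censored after unblinding or AV, and no formal testing of safety data is planned. All of this stands, and it confines the harm within a single table to the accompanying event count. It does not reach changes that cross a boundary: the once-per-subject rule works within a table and the protocol rule within one 28-day window, so neither removes the extra subject from the dose 2 table in A or the double entry in C.

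A reader might infer that events are moved out of their proper group. For severity changes they are not: the original record keeps its date, dose and group, and the event is duplicated.

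A reader might also infer that an early related SAE can vanish from its window, for example one on Day 5 judged unrelated and re-assessed as related on Day 60. The documents do not support that as a demonstrated loss. Under Protocol Appendix 10 the revised opinion goes into the original entry, so the SAE stays at Day 5 and becomes related. A change from unrelated to related is also an increase, so it is not an instance of the gap between increase and any change. What remains is that SAP 10.5.1 and Protocol Appendix 10 describe different recording practices and must be reconciled.

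**Conclusion.** The inconsistency in SAP 10.5.1 is real. Followed literally, it gives wrong results for unsolicited AEs, SAEs, AESIs and medically attended AEs. Each improvement or downgrade adds one event. When it falls after dose 2, it also adds the subject to the dose 2 table and that dose's 28-day window. When it falls after an AV, it places the event in two exposure groups, but only in the 12.7.7 outputs.

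Two stronger conclusions are tempting and not supported. One is that the percentages of subjects forming the primary safety estimand are inflated generally; within a single table they are unchanged. The other is a figure such as 10–30% inflation of event counts; the documents give no frequency of decreases or downgrades, so the multipliers shown are illustrations only. Solicited AEs are largely outside the problem, except that overlapping records with different relationships are not collapsed.

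The conclusion assumes that CRF records are opened as SAP 10.5.1 describes. If sites updated the original entry as Protocol Appendix 10 directs, fewer events would be split. The documents do not show which practice was followed. The point merits correction because the rule is explicit and the 12.7.7 outputs stand in for the open-label safety analyses.

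**What to change.** Amend SAP 10.5.1 as follows.

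- Treat only an increase in severity as a new TEAE with a new start date, attributed to the dose or exposure group at the time of the increase. Assigning every record by first onset would instead hide a genuine worsening after dose 2 or an AV.
- Link any record that reflects a decrease in severity or a causality update to the original event. Keep the original onset date and count the event once, at maximum severity and with the most recent investigator assessment of relationship. The definition should then no longer treat a change of relationship as making an event treatment-emergent.
- For linked records, base the dose, reporting window and 12.7.7 group on the original onset.
- Reconcile 10.5.1 with Protocol Appendix 10 on where updates are recorded.

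The cost is SAP wording and a record-linking step in the AE dataset, with a check that linked records are the same event. No new data are needed. The documents do not say whether split CRF records already carry a link, so the effort of that check cannot be judged from them.

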10.3 Missing Data

In general, no imputation of missing values is done except for the following:

- Imputation of missing onset date for confirmed COVID-19 cases as specified in Section 10.7.2.
- For SARS-CoV-2 RBD of S protein antibodies, and viral neutralizing antibodies, concentration values marked as below the lower limit of quantification (LLOQ) are set to 0.5*LLOQ for computation purposes.
- Imputation of (partially) missing AE start dates:
 - If start date year value is missing, the date uncertainty is too high to impute a rational date. Therefore, if year value is missing, the imputed AE start date is set to missing.
 - If start date year value is before the vaccination start date year value, then the AE started before the vaccination. Therefore:
 - If month is missing, the imputed start date is set to the mid-year point (i.e., 01JULYYYY).
 - If month is not missing, the imputed start date is set to the mid-month point (i.e., 15MONYYYY).
 - If start date year value is equal to the vaccination start date year value, the start date month needs to be compared against the vaccination start date month, to determine the imputation rule to apply. Therefore:
 - If month is missing, the imputed month and imputed day is the same as start of vaccination
 - If month is lower than vaccination start date month and start date day is missing, the imputed start date is set to the mid-month point (i.e. 15MONYYYY).
 - If month is equal to the vaccination start date month and start date day is missing, the start day is set to the start day of vaccination.
 - If month is greater than the vaccination start date month and start date day is missing, the imputed start date is set to the beginning of the month (i.e., 01MONYYYY).
 - If start date year value is greater than the vaccination start date year value, the AE started after vaccination. Therefore:
 - If month is missing, the imputed start date is set to the year start point (i.e., 01JANYYYY).
 - If start date month is not missing and start date day is missing, the imputed start date is set to the beginning of the month (i.e., 01MONYYYY).
 - If after imputation of start and resolution date (see below) a start date is after the resolution date (for example if a missing day of a start date is set to 15 and the resolution date is before the 15th of the same month and year) then the start date is set to the resolution date.
- Imputation of (partially) missing AE end dates:

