 - If date of resolution is completely missing, and it is assumed that it resolved at the date of the end of the trial, the date of the end of the trial is used as the AE end date.
 - If year is present, it is assumed that it resolved on 31 December of that year (i.e., 31DECYYYY), or at the end of the trial if this is earlier and in the same year.
 - If year and month are present, it is assumed that it resolved on the last day of that month, or at the end of the trial if this is earlier and in the same month/year.
- Imputation of missing AE start times:
 - If the (recorded or imputed) AE start date is equal to the vaccination start date, then the AE start time is the time of vaccination start.
 - In all other cases, AE start time is imputed as 00:00.

If not stated otherwise, the original or incomplete data is presented in listings rather than the imputed one.

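### Read literally, the TEAE rule drops unsolicited AEs whose start is imputed to the exact date and time of first vaccination

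*SAP*

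**What the plan says.** SAP 10.5.1 sets the date test for treatment emergence: "an AE is defined as TEAEs if the start date/time is after the date/time of first CVnCoV/placebo vaccination". The same section adds that "Imputed AE start date/time as defined in Section 10.3 is considered when assessing if an AE is treatment emergent".

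SAP 10.3 then supplies the imputed values. Its rule for a missing time covers observed and imputed dates alike; when an event's "AE start date is equal to the vaccination start date, then the AE start time is the time of vaccination start". Every other missing time becomes midnight. For a partial date in the year of vaccination, "If month is missing, the imputed month and imputed day is the same as start of vaccination". Where the month is known and is the vaccination month but "start date day is missing, the start day is set to the start day of vaccination".

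SAP 12.7.1 makes the result count: "Only TEAEs as defined in Section 10.5.1 are included in AE summaries". AE listings keep every event.

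SAP 10.5.1 has two exemptions. Solicited AEs are always treatment emergent, whatever their dates look like. An AE whose start year is missing is also treated as emergent.

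**The concern.** The imputation and the test do not fit together. The imputation places a doubtful event exactly at vaccination, and the test accepts only events later than that. An unsolicited AE with an imputed start at the vaccination time therefore fails, and no other section of the SAP rescues it.

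The counts at stake belong to primary safety endpoints (SAP 9.1.2): unsolicited AEs, SAEs, AESIs, medically-attended AEs and AEs leading to withdrawal. Their estimands (SAP 9.5) are numbers and percentages of subjects, which come from the summary tables.

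The exemption for solicited AEs gives no cover in Phase 3, because solicited AEs are collected only in Phase 2b. Phase 3 is planned at 32,500 of 36,500 subjects (32,500 / 36,500 = 89%). Events on the day of vaccination are collected there by design: Protocol 9.3.3 requires AESIs, medically-attended AEs and SAEs in the 30-minute observation period to be recorded. Anaphylaxis is on the AESI list (SAP Appendix 2). An unsolicited anaphylaxis entered on the first-vaccination day without a start time would, on the literal text, be missing from the AESI counts.

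**Working it through.** The plan gives no figure to reproduce, so the check applies the SAP rules to example dates.

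**Inputs.** The start-date and start-time imputations are from SAP 10.3, and the test and its exemptions from SAP 10.5.1. The example first vaccination, 20 January 2021 at 10:30, is assumed.

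**Test.** As written, an AE is a TEAE if start > vaccination. The alternative is start ≥ vaccination. The table covers unsolicited AEs.

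| Recorded start | Start used in the test | TEAE with > | TEAE with ≥ |
|---|---|---|---|
| 20 Jan 2021, no time | 20 Jan 2021 10:30 | No | Yes |
| Jan 2021, day missing | 20 Jan 2021 10:30 | No | Yes |
| 2021, month missing | 20 Jan 2021 10:30 | No | Yes |
| 20 Jan 2021, 11:00 | 20 Jan 2021 11:00 | Yes | Yes |
| 20 Jan 2021, 09:00 | 20 Jan 2021 09:00 | No | No |
| 21 Jan 2021, no time | 21 Jan 2021 00:00 | Yes | Yes |
| Feb 2021, day missing | 1 Feb 2021 00:00 | Yes | Yes |
| Year missing | none | Yes (exempt) | Yes (exempt) |

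Three of the eight patterns change with the operator. The event timed at 09:00, before vaccination, stays out under both. For solicited AEs all eight patterns are TEAEs under either operator, because of the exemption.

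**Does ≥ let in events known to precede vaccination?** It does not, as long as the 10.3 rules are kept.
- Dec 2020, day missing: the year precedes the vaccination year, so the start becomes 15 Dec 2020, which is before 20 Jan 2021. Excluded.
- Jan 2021, day missing, resolved 12 Jan 2021: the start is first set to 20 Jan. That is after resolution, so 10.3 resets it to 12 Jan. Excluded.

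**Is the exclusion intended?** The SAP's own text points the other way.
- An AE with no year counts, while an AE known to fall in the vaccination year with no month does not. For the example subject, 365 − 20 = 345 of the 365 days of 2021 lie after the vaccination day, yet an AE dated only 2021 is dropped.
- For dose 2, SAP 10.5.4 assigns same-day unsolicited AEs at or after the injection to dose 2, and does the same when the order cannot be established. First-dose AEs of unknown order get the opposite treatment.
- Protocol 10.3.7 sends AEs that start before first vaccination to medical history, so an untimed AE record on the vaccination day is presumably post-vaccination.

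**A related boundary.** SAP 12.7.7 allocates each AE to one of four groups according to what was administered before the AE start date. On the first-vaccination day no trial dose has an earlier date. On a literal reading, an AE on that day can therefore fit none of the four groups.

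**The case against.** The best defence is that the intent is plain. Giving these events the vaccination time, when every other missing time becomes midnight, makes sense only if they were meant to count. The unsolicited-AE summaries named in SAP 6.2 include the day of vaccination. A programmer may well have used 'on or after', and the programs are not in the documents. This stands as evidence of intent. It does not cure the text, which is what the derivation should follow.

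It can also be said that the reach is limited. The reactions most expected on the vaccination day in Phase 2b are solicited and exempt, and the SAE, AESI, medically-attended and withdrawal lines of the overall summary in SAP 12.7.1.3 include solicited AEs. Missing data are queried (Protocol 11.4), and initial SAE reports should give an onset date (Protocol Appendix 10). Safety is descriptive, with no formal test (Protocol 10.3.7), and no efficacy criterion uses the TEAE flag. All of this stands. It limits the likely number of affected events, but it does not show that the number is zero, and complete listings do not correct a count in a table.

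**Conclusion.** The rule is wrong as written and needs correcting. The affected group is confined to unsolicited AEs whose start is imputed to exactly the date and time of first vaccination. Its size is unknown, because the documents give no count of untimed or partly dated AEs. The conclusion rests on reading 'after' literally.

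Three stronger readings are tempting, and the documents do not support them.
- A reader might infer that all untimed or partly dated AEs on the vaccination day disappear from every AE table. Solicited AEs and AEs with no start year are exempt, and nothing disappears from the listings.
- A reader might infer that some percentage of events is lost, or that the vaccine arm loses more. No figure supports a percentage. The rule is the same in both arms, and solicited reactogenicity is outside it.
- A reader might infer that delivered tables are known to be wrong. Only the text is available, so this has to be checked.

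**What to change.** In SAP 10.5.1 change 'after' to 'on or after', so that an AE is treatment emergent if its start date/time ≥ the date/time of first vaccination. Keep the 10.3 imputations as they are. AEs whose recorded date parts, recorded time or resolution date show onset before vaccination then stay excluded. Do not replace this with a rule that excludes only fully recorded pre-vaccination starts: it would admit events such as the December 2020 example, whose date is imputed but known to be too early.

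In SAP 12.7.7, check that AEs on the first-vaccination day fall into a group, and state the rule for that day explicitly.

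Count the records that match the three affected patterns, and check them against safety tables already delivered, including any from the interim analyses and the Phase 2b six-week delivery. Rerun a table only where the literal rule was programmed and a count changes.

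The text change is a few words and one operator in the derivation. The real cost is checking past outputs. SAP version 5.0 was written by an unblinded team (SAP 6.1), but the change applies identically to both arms, and safety outputs through end of trial are still planned (SAP 12.7.1.4 and 12.7.7).
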